9.2. Exposure to Study Drug

The number and percentage of patients with dose administered at each treatment visit will be tabulated by treatment group for the Safety population. For patients who are not administered, reason why the dose was not administered will be also displayed. Planned dose per BSA (mg/m^2), actual administered dose per BSA (mg/m^2), actual dose intensity (actual administered dose per BSA / actual duration of dose) ($\text{mg}/\text{m}^2/\text{week}$) and relative dose intensity (actual dose intensity / planned dose intensity * 100) (%) will be summarized using descriptive statistics by visit.

Actual duration of dose is given by the following formula:

$$\text{Actual duration of dose (Weeks)} = (\text{Next cycle date} - \text{Current cycle date}) / 7$$

For the last cycle within each study period, the duration of dose is assumed to be 1 week for the Induction Study Period and 8 weeks for the Maintenance Study Period.

For those patients action taken, the number and percentage of patients with each reason (AE or Other) will be displayed by visit. The proportion of patients who are administered incorrect dose will be summarized on the table. Incorrect dose is defined as an actual dose level which is 5% over than planned dose (mg/m^2) * BSA (m^2). Moreover, for those patients delaying study drug, the number and percentage of patients with each reason (Nonhematological toxicity, Hematological toxicity, Cardiac toxicity, Other adverse event, Disease evaluation and Other) will be displayed.

Total number of patients with at least one dose (Full/Partial) of study drug during Overall will be summarized. Descriptive statistics of the total amount of planned dose per BSA (mg/m^2) and actual administered dose per BSA (mg/m^2), actual dose intensity ($\text{mg}/\text{m}^2/\text{week}$) and relative dose intensity (%) will also be provided displaying.

The total actual duration of dose will be based on the following calculation:

$$\text{Duration of dose for Overall (Weeks)} = \text{Duration of dose for up to MP1 (Weeks)} + \text{Duration of dose for MP2 (Weeks)}$$

$$\text{Duration of dose for up to MP1 (Weeks)} = (([\text{Last infusion date during Induction Study Period} + 7] - \text{First infusion date during Induction Study Period}) / 7) + (([\text{Last infusion date during MP1} + 56] - \text{First infusion date during MP1}) / 7)$$

$$\text{Duration of dose for MP2 (Weeks)} = ([\text{Last infusion date during MP2} + 56] - \text{First infusion date during MP2}) / 7$$

during MP2) / 7

In addition, a listing will be provided by treatment group for the Safety population showing the details of study drug exposure for each patient including BSA.

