4. OVERALL STUDY DESIGN AND PLAN

This is a Phase 3, prospective, randomized, parallel-group, active-controlled, double-blind, multicenter, international study to evaluate the similarity of efficacy and safety of CT-P10 to Rituxan in patients with Grade 1 to 3a (Ann Arbor stage II-IV) low tumour burden follicular lymphoma (LTBFL) based on Groupe d'Etudes des Lymphomes Folliculaires (GELF) criteria. The study will include study centers in Europe, Africa, the Middle East, Asia Pacific, and Latin and North America.

The study will consist of 4 periods: Screening Period, Induction Study Period, Maintenance Study Period, and Follow-up Period. The overview of study design is shown in [Figure 1](#).

Figure 1: Schematic of Study Design

- Screening Period (up to 6 weeks)
- Induction Study Period (up to 4 weeks):
 - Study drug will be administered weekly for 4 weeks (at a dose of 375 mg/m² by an intravenous [IV] infusion).
 - The End of Treatment (EOT) 1 visit will occur 1 week (±1 day) after the last dose of study drug administration in the Induction Study Period.
 - Patients will be assessed 8 weeks (±7 days) after the last dose of study drug administration in the Induction Study Period, and the investigator will determine whether patients qualify to continue in the Maintenance Study Period.
 - Patients who experienced CR, CRu, PR, or stable disease (SD) in this assessment will qualify for the Maintenance Study Period and the assessment visit will be called the Maintenance 1 visit.
 - Patients who experienced progressive disease (PD) or unknown status of disease will not enter into the Maintenance Study Period. These patients will be withdrawn from the study treatment and will enter the Follow-up Period, provided patient consent has not been withdrawn. For these patients, the assessment visit will be called the EOT2 visit.

- If a patient withdraws before the completion of the Induction Study Period, this patient will not enter the Maintenance Study Period. However, the patient will enter the Follow-up Period, provided patient consent has not been withdrawn.
- Maintenance Study Period (up to maximum 12 cycles for 2 years):
 - The first dose in the Maintenance Study Period will be administered 8 weeks (± 7 days) after the last dose of study drug administration in the Induction Study Period.
 - Study drug will be administered every 8 weeks up to maximum 12 cycles for 2 years (at a dose of 375 mg/m^2 by an IV infusion).

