 - The first year of Maintenance Period (MP1) consists of 6 cycles of maintenance therapy (Maintenance Cycles 1 to 6) and the second year of Maintenance Period (MP2) consists of 6 cycles of maintenance therapy (Maintenance Cycles 7 to 12). After MP1, once the similarity between study drugs is confirmed, additional treatment with CT-P10 will be offered to all patients who have completed MP1 at discretion of the investigator.
 - The EOT3 visit will occur 8 weeks (± 7 days) after the last dose of study drug administration in the Maintenance Study Period.
 - Patients who complete the Maintenance Study Period will enter the Follow-up Period. A patient will be considered as having completed the study treatment if:
 - The patient could have entered but did not continue on the MP2 and completed all visits of the MP1 (total 6 cycles).
 - The patient continued on the MP2 and completed all visits of the MP1 and MP2 (total 12 cycles).
 - If a patient withdraws before the completion of the Maintenance Study Period, the patient will enter the Follow-up Period, provided patient consent has not been withdrawn.
 - If a patient is terminated within 6 months from Day 1 of Cycle 1 of the Induction Study Period, the EOT3 visit will occur within 4 to 8 weeks (± 7 days) after the last dose of study drug administration in the Maintenance Study Period.
- Follow-up Period (up to 27 months from Day 1 of Cycle 1 of the Induction Study Period for the last enrolled patient):
 - During the Follow-up Period, patients will be monitored every 6 months (± 2 weeks) for disease status until treatment with new anticancer therapy or disease progression, and

every 3 months (± 2 weeks) for survival and salvage treatment until death or study termination.

The end of study is defined as the date of the database is locked. The schedule of events is presented in [APPENDIX 1](#).

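### The Overall actual dose intensity in SAP 9.2 pools weekly Induction with 8-weekly Maintenance, so it cannot be compared between patients with different numbers of cycles

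*SAP*

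**What the plan says.** SAP section 4 sets two dosing rates at the same dose of 375 mg/m2. In Induction, "Study drug will be administered weekly for 4 weeks". In Maintenance, "Study drug will be administered every 8 weeks up to maximum 12 cycles for 2 years". The number of cycles differs between patients by design:

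- Patients with progressive disease or "unknown status of disease will not enter into the Maintenance Study Period".
- After MP1, "additional treatment with CT-P10 will be offered to all patients who have completed MP1 at discretion of the investigator".
- A patient who takes 6 Maintenance cycles and no MP2 still counts as having completed treatment.

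SAP 9.2 defines "actual dose intensity (actual administered dose per BSA / actual duration of dose") in mg/m2/week, and relative dose intensity (RDI) as actual over planned intensity, times 100. Both are summarised by visit and again at Overall level, in the paragraph that opens "Total number of patients with at least one dose (Full/Partial) of study drug during Overall will be summarized" and closes by saying that actual dose intensity "and relative dose intensity (%) will also be provided displaying". Overall duration is the sum of three terms: Induction (first to last infusion plus 7 days), MP1 (first to last plus 56 days) and MP2 (first to last plus 56 days). The section does not say what planned dose intensity means for Overall.

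The same paragraph also plans the total planned and total actual dose per BSA. Earlier in 9.2, patients dosed at each visit are tabulated by treatment group.

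**The concern.** A dose intensity is meant to show how closely the dosing delivered kept to the planned rate. Here the planned rate changes eightfold between periods. The pooled ratio therefore mainly reflects how many Maintenance cycles a patient had, and it falls as that number rises. A patient who leaves after Induction looks more intensively dosed than one who completes the course.

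Exposure tables give the context for the comparison of efficacy and safety between CT-P10 and Rituxan. If one arm has more early stopping or lower MP2 uptake, its mean Overall intensity goes up although its patients received less drug. A reader of the table would then see two rows that disagree, with nothing in the SAP to explain why.

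**Working it through.** The documents state no dose-intensity figure, so there is none to reproduce. The check applies the SAP's own formulas.

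**Inputs.** Dose 375 mg/m2; Induction weekly, 4 infusions; Maintenance every 8 weeks, up to 6 in MP1 and 6 in MP2 (SAP 4). Duration and intensity formulas from SAP 9.2. Assumptions: full doses on schedule, and a period with no infusions adds zero weeks.

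**Duration.** For i Induction infusions, ((i − 1) × 7 + 7) / 7 = i weeks. For m Maintenance infusions, MP1 and MP2 together give 8m weeks.

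**Overall actual dose intensity** = 375 × (i + m) / (i + 8m).

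Each further Maintenance cycle adds dose at 375 / 8 = 46.9 mg/m2/week, which is below the running average, so the ratio falls at every cycle.

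| Course received | Total dose (mg/m2) | Weeks | Overall intensity (mg/m2/week) |
|---|---|---|---|
| Induction only (4) | 1500 | 4 | 375 |
| 4 + 1 | 1875 | 12 | 156.25 |
| 4 + 2 | 2250 | 20 | 112.5 |
| 4 + 6 (full MP1) | 3750 | 52 | 72.1 |
| 4 + 12 (full MP1 + MP2) | 6000 | 100 | 60.0 |

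Induction only against all 16 infusions: 375 / 60 = 6.25 times the intensity on 1500 / 6000 = one quarter of the dose. Two fully adherent completers, one with MP2 and one without, score 60 and 72.1.

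**Overall RDI for an Induction-only patient**, under three readings of the undefined planned intensity:

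- plan matched to the cycles started: 375 / 375 = 100%
- fixed 10-dose plan: 375 / 72.1 = 520%
- fixed 16-dose plan: 375 / 60 = 625%

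**Effect on arm means (assumed rates; the documents give none).** Suppose 5% of one arm and 10% of the other stop after Induction, and everyone else receives 16 infusions.

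- Mean intensity: 0.05 × 375 + 0.95 × 60 = 75.75, against 0.10 × 375 + 0.90 × 60 = 91.5, which is 21% higher.
- Mean total dose: 0.05 × 1500 + 0.95 × 6000 = 5775, against 0.10 × 1500 + 0.90 × 6000 = 5550 mg/m2, which is lower.
- Data up to Month 7 (the 1st CSR cut-off, SAP 2.1), others at 4 + 2: 0.05 × 375 + 0.95 × 112.5 = 125.6, against 0.10 × 375 + 0.90 × 112.5 = 138.8, about 10% higher.

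**Is this only the interval between periods?** On schedule, the Overall formula leaves out 7 weeks between the end of Induction (last infusion + 7 days) and Maintenance Cycle 1. With those weeks restored, the values are 1500 / 11 = 136.4 (Induction only), 2250 / 27 = 83.3 (4 + 2), 3750 / 59 = 63.6 (full MP1) and 6000 / 107 = 56.1 (all 16). The order is unchanged, but the 5% against 10% example shrinks to 60.1 against 64.1, about 7%.

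**By period.** Computed separately, on-schedule intensity is 375 in Induction and 46.9 in MP1 and MP2, whenever the patient stops.

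**The case against.** The case for leaving the section alone is that one row is awkward while the rest of the exposure reporting is sound. Much of that stands.

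- A reader might infer that the planned exposure comparison as a whole ranks the least-treated patients highest. It does not. Total administered dose is in the same sentence and ranks them correctly, patients dosed per visit are tabulated, and by-visit intensities do not mix the two rates.
- A reader might infer that Overall RDI is also reversed. The documents do not establish this. Matched to the cycles started, RDI is 100% for every on-schedule patient and drops with delays or reductions, which is its purpose. The 520% and 625% figures need a fixed full-course plan that the SAP does not state. The fault is a missing definition.
- A reader might infer that an earlier stop always gives a higher figure. Stops after 1, 2, 3 or 4 Induction infusions all give 375, and delays lower it: four Induction infusions at 14-day intervals give 1500 / 7 = 214.
- A literal sum might seem to drop patients who have no MP1 or MP2 dates. Counting an absent period as zero is the ordinary reading, and the 375 for Induction-only patients depends on it.
- The size depends on the scenario. The 5% and 10% rates are assumed, and the median in that 16-infusion example is 60 in both arms. A 10-point difference in MP2 uptake moves the mean by only 0.10 × (72.1 − 60) = 1.2 mg/m2/week.
- No test or decision rule uses the table, and SAP 6 reports disposition by period.

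None of this makes the Overall actual intensity row interpretable.

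**Conclusion.** The point holds for Overall actual dose intensity. Among patients dosed in full and on schedule it runs from 375 mg/m2/week (Induction only) down to 60 (16 infusions), opposite to total dose, and it cannot be compared across patients with different numbers of cycles. Arm summaries are distorted only if early stopping or MP2 uptake differs between arms. Under the assumed 5% against 10% split, the arm given less drug shows a mean higher by about 7% to 21%, depending on the data cut and on whether the 7-week interval is counted.

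For Overall RDI the conclusion is limited to the missing definition: the same patient can score 100%, 520% or 625%. The primary response analysis and the other exposure summaries are untouched. This is a fault in one descriptive row that is worth correcting because the correction is easy.

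**What to change.** In SAP 9.2:

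1. Replace the Overall actual dose intensity with actual dose intensity and RDI summarised separately for Induction, MP1 and MP2, each in patients dosed in that period and against the schedule already planned for that period.
2. For Overall, keep the total administered dose per BSA that is already planned and add the number of infusions received.
3. If an Overall RDI is kept, define its planned intensity as that of the cycles the patient started.

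This fits the SAP's existing practice of reporting concomitant medications (9.1) and adverse events (13.1) by period. The cost is SAP wording and a few extra rows in one table. No new data are needed.

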9.3. Salvage Treatment

During the Follow-up Period, salvage treatment (e.g., including chemotherapy, immunotherapy, radiotherapy or surgery) will be monitored every 3 months until death or study termination. Chemotherapy and immunotherapy will be coded according to the WHO DD September, 2015 or later, and surgery will be coded using MedDRA version 18.1 or later.

Therapy details will be listed and tabulated by therapy category and treatment group for the Safety population. Drug class (using ATC level 2) and PT will be used for chemotherapy and immunotherapy. Type of radiotherapy and purpose of surgery will be summarized for radiotherapy and surgery respectively. SOC and PT will be used for surgery.

10. EFFICACY ANALYSES

Efficacy will be assessed by response evaluation, and time-to-event analyses. Sensitivity analysis for response evaluation will also be performed.

Response evaluation will be based on the tumour assessment using image, bone marrow involvement, organ enlargement, lactate dehydrogenase (LDH) level and B-symptoms according to the Modified Response Criteria for Malignant Lymphoma. Tumour assessments will be performed at the time points specified in the [APPENDIX 1](#).

Images for tumour assessment will be reviewed twice by central and local, and both image review results from central (central independent reviewer) and local (eCRF) will be analyzed and listed separately.

Listings based on central independent review and local review including target lesions, non-target lesions and new lesions will be presented by treatment group and visit for ITT population respectively. Patients who are included in the PP population will be flagged in listings. The target lesions listing collected from central review will include following: Information of lesion number, tumour type, location, laterality, methods of measurement, days of assessment, shortest and longest axis (mm), product of the perpendicular diameters (PPD) of target lesions (mm²), sum of product of the perpendicular diameters (SPD) of target nodal lesions (mm²), percent change from baseline of target nodal SPD (%), percent change from nadir of target nodal SPD (%). SPD, percent change

from baseline of SPD and percent change from nadir of SPD for target extra-nodal and both (target nodal and target extra-nodal) also will be listed. The target lesions listing from local review will include following: Information of lesion number, location, site code, days of assessment, methods of measurement, shortest and longest axis, PPD and SPD

Listings for response evaluation results from central and local will be presented separately. Both listings will include best overall response (BOR) and BOR date (prior to MC3). For central response evaluation results, most recent date will be derived as the date of response evaluation based on the following considerations:

Overall Response Evaluation	Radiologic Response ¹	Bone Marrow	B-symptom	LDH Level
CR	√	√	√	√
CRu	√	√	√	√
PR	√	√ ²	√ ³	√ ³
SD	√	√ ²		

Note: Date of progression disease and relapsed disease will be determined as recorded date of oncologist evaluation.

1 Date of target lesion, non-target lesion and new lesion assessment will be included.

2 For PD case exclusion.

3 It will be considered when overall response is downgrade from CR or CRu.

Response date of central review will be used for BOR date of central. Also, date of evaluation recorded on the ‘Response Evaluation’ eCRF page will be used for BOR date of local response evaluation results. If BOR of two or more assessment visits are same, then the BOR of the earliest assessment date will be used. Listings will be produced for the ITT population including PP population flag.

10.1. Primary Efficacy Endpoint

The primary efficacy endpoint is the ORR (CR + CRu + PR) at 7 months (Prior to Cycle 3 of the Maintenance Study Period) according to the Modified Response Criteria for Malignant Lymphoma.

10.1.1. Overall Response Rate

Overall response rate (ORR) is defined as the proportion of patients whose BOR is CR, CRu or PR (the ‘responders’). For the primary analysis, the BOR will be derived from the overall responses according to the Modified Response Criteria for Malignant Lymphoma across all time points up to 7 months assessment (Prior to Cycle 3 of the Maintenance Study Period). When CR, CRu, PR or SD is believed to be the best response, it must also meet the minimum 8 weeks from randomization. If the minimum duration is not met in case of CR, CRu, PR or SD, the patient’s BOR will be decided as the best response among subsequent assessments fulfilled the minimum

duration. For example, a patient who has SD at first assessment, progressive disease at second and does not meet minimum duration for SD, will have a best response of progressive disease. If the patient lost to follow-up after the first SD assessment, the patient's overall response would be considered to be unevaluable. In the case when a patient has an assessment result of PD within the minimum duration of 8 weeks from randomization, the patient's BOR will be considered as PD.

ORR up to 7 months will be compared between CT-P10 group and Rituxan group for the ITT population and PP population. A point estimate and 90% CI of the difference between two proportions will be presented using an exact binomial method. Similarity will be demonstrated if the two-sided 90% CI for the difference in proportion between CT-P10 and Rituxan is within the equivalence margin of $\pm 17\%$. Additional exact binomial test will be conducted for ITT population – ADA Negative/Positive subset and PP population – ADA Negative/Positive subset. If the number of ADA Positive subset is very small ($\leq 5\%$ of ITT population or PP population) then the subset will not be summarized since it is not statistically meaningful.

A table presenting ORR and the analysis result will be provided. The number and percentage of patients in each response category will also be presented by treatment group separately. Patients without any response evaluation data will be included as 'Missing'. A supportive analysis will be conducted in the PP population and also be provided in the table. The table will be generated by using data from the central review and the local review separately. Additional table presenting ORR will be shown for ITT population – ADA Negative/Positive subset and PP population – ADA Negative/Positive subset. If the number of ADA Positive subset is very small ($\leq 5\%$ of ITT population or PP population) then the subset will not be summarized since it is not statistically meaningful.

10.1.2. Sensitivity Analysis

As the exact binomial method does not allow for stratification, a sensitivity analysis will be performed on the primary efficacy endpoint, utilizing a logistic regression model with treatment as a fixed effect and region (Asia Pacific vs. Europe vs. North America and Other), Ann Arbor stage (Lower than or equal to II vs. III vs. IV) and age (≥ 60 vs. < 60 years) as covariates. The resulting odds ratio and 90% CI will be converted into difference of proportions using the Delta method for the purpose of comparison of proportions. The sensitivity analysis will be conducted in the ITT population and the PP population supportively.

Difference of proportions using the Delta method is explained in the following process.

- 1) The individual odds and standard errors (SEs) for both treatments will be obtained from the model. For the purposes of this algorithm, let the estimate of the odds of being a responder in the CT-P10 group be denoted by θ_a and the estimate of the odds of being a

responder in the Rituxan group be denoted by θ_b

- 2) Calculate the variances of these estimates, $\text{Var}(\theta_a)$ and $\text{Var}(\theta_b)$ respectively from the SEs obtained from the model.
- 3) Calculate the estimates of the corresponding proportions, denote p_a and p_b respectively, for each of the treatment groups, from the estimated odds using the following formula:

$$p_a = \frac{\theta_a}{1 + \theta_a}, \quad p_b = \frac{\theta_b}{1 + \theta_b}$$

And hence calculate the estimate of the difference of proportions ($p_a - p_b$).

- 4) Using Taylor expansions and the Delta method, the following formula for approximation can be obtained:

$$\text{Var}[f(X)] \approx (f'(E[X]))^2 \text{Var}[X]$$

Applying this approximation specifically to this case, and using the formula specified in step (3) we obtain the formula

$$\text{Var}(p_a) = \frac{\text{Var}(\theta_a)}{(1 + \theta_a)^4}, \quad \text{Var}(p_b) = \frac{\text{Var}(\theta_b)}{(1 + \theta_b)^4}$$

Which should be used to calculate $\text{Var}(p_a)$ and $\text{Var}(p_b)$.

- 5) Calculate the variance of the difference in proportions $\text{Var}(p_a - p_b)$ as the sum of $\text{Var}(p_a)$ and $\text{Var}(p_b)$. Use this to obtain the SE of the difference, and hence calculate the 90% CI using the formula:

$$90\% \text{ Confidence Interval} = (p_a - p_b) \pm 1.64 [\text{SE}(p_a - p_b)]$$

Note: this method assumes that the estimate ORR of CT-P10 group is independent of the estimate ORR of the Rituxan group.

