5.2. Sample Size

Sample size calculations for the primary efficacy endpoint are based on the proportion of patients with a CR, CRu, or PR response (the “responders”) at 7 months (Prior to Cycle 3 of the Maintenance Study Period).

A sample size of 174 patients (87 patients in each treatment group of CT-P10 and Rituxan) leads to 91% statistical power for the demonstration of similarity of ORR at 7 months (Prior to Cycle 3 of the Maintenance Study Period) based on ORR of 88% and an equivalence margin of $\pm 17\%$ using a 2-sided 90% CI approach corresponding to 5% significance level of an equivalence test. The intent-to-treat (ITT) population will be the primary analysis population for the efficacy analysis. A supportive analysis for the efficacy analysis will be conducted using the per-protocol (PP) population for response rate. In the PP population with a 13% drop-out rate, 86% statistical power is expected.

The equivalence margin of $\pm 17\%$ preserves at least 77% efficacy based on the lower bound of 95% CI of the estimated difference of ORRs of patients received rituximab 6 doses (88%, 162/184) and of patients in “watch-and wait” group (6%, 9/155) in Ardeshtna et al (2014). The historical efficacy of rituximab based on the difference of ORR between the patients treated with rituximab and patients in “watch-and wait” group is 82% with the 95% CI of (0.75, 0.88). Therefore, the historical treatment efficacy of rituximab for the equivalence margin is estimated as 75% conservatively and by applying 77% preservation rate, the equivalence margin is proposed as $\pm 17\%$.

The actual drop-out rate and ORR will be assessed in a blinded manner at data safety monitoring board (DSMB) when the primary endpoint evaluation is available from 50%-60% of patients. A reassessment of sample size accounting the actual drop-out rate and the observed ORR in blinded

manner will be made in order to achieve an adequate statistical power for the primary endpoint; at least 80% power in PP population. The sample size will not be decreased from the initial 174 total sample size but could be increased up to 250 patients.

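### The step 1–5 confidence interval in SAP 10.1.2 fails if a region or stage level contains only responders, and the SAP has no fallback

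*SAP*

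**What the plan says.** SAP 10.1.2 explains that the exact binomial method cannot be stratified. It therefore adds a sensitivity analysis of the primary endpoint "utilizing a logistic regression model with treatment as a fixed effect and region (Asia Pacific vs. Europe vs. North America and Other", with Ann Arbor stage in three levels and age in two, for the ITT population and supportively for PP.

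Step 1 of the conversion reads: "The individual odds and standard errors (SEs) for both treatments will be obtained from the model". Steps 2–5 turn each arm's odds into a proportion, obtain each variance by the delta method, add the two variances and form a 90% CI for the difference.

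The section does not state the covariate values at which an arm's odds are evaluated. It has no rule for separation, non-convergence or sparse levels. Some pooling is already planned: North America with Other, and stage II with anything lower.

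SAP 5.2 sets the size: "A sample size of 174 patients (87 patients in each treatment group of CT-P10 and Rituxan) leads to 91% statistical power", "based on ORR of 88% and an equivalence margin of" ±17%. For PP: "In the PP population with a 13% drop-out rate, 86% statistical power is expected". After a blinded reassessment the sample "could be increased up to 250 patients". SAP 10.1.1 bases the similarity conclusion on the exact binomial 90% CI, not on this model.

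**The concern.** With a high response rate, non-responders are the scarce outcome, and they are spread over two three-level factors as well as age and treatment. A small region or stage level can easily contain none. An ordinary logistic fit then pushes that level's coefficient towards infinity, and its standard error with it.

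Steps 1–5 do not work from the treatment odds ratio alone. They need the absolute odds in each arm. If those odds are averaged over covariate levels, they carry the diverging coefficient into both the estimate and the variance. The only planned stratification-adjusted check on the primary result would then return an interval on the difference scale that says nothing about the data, with no stated alternative.

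**Working it through.** **The plan's own figure.** Inputs from SAP 5.2: 87 per arm, ORR 88% in both arms, margin 0.17, "using a 2-sided 90% CI approach corresponding to 5% significance level of an equivalence test". By normal approximation, SE = √(2 × 0.88 × 0.12 / 87) = 0.0493, and power = 2Φ(0.17/0.0493 − 1.645) − 1 = 92.9%. Full binomial enumeration gives 91.1% with the score test and 90.8% with the exact unconditional test. For PP at 75–76 per arm the score test gives 85.5–86.6% and the exact test 85.1%. The stated 91% and 86% are reproduced, so 88% and 174 are sound inputs.

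**Effects and events.**
- Effects: treatment 1 + region 2 + stage 2 + age 1 = 6, plus the intercept.
- ITT: 174 × 0.12 = 20.9 non-responders (90% binomial range 14–28), or 3.5 per effect.
- PP: 174 × 0.87 ≈ 151 patients; 151 × 0.12 = 18.1, or 3.0 per effect.
- Maximum size: 250 × 0.12 = 30, or 5.0 per effect.

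**Chance of an all-responder level at ORR 88%.** For a level of exactly n patients it is 0.88^n: n = 9, 32%; n = 17, 11%; n = 26, 3.6%; n = 35, 1.1%. If a level has share q and its size varies, it is (1 − 0.12q)^174:
- q = 5%: 0.994^174 = 0.35
- q = 10%: 0.988^174 = 0.12
- q = 20%: 0.976^174 = 0.015
- q = one third: 0.96^174 = 0.0008

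For any level in the model, simulated with 4,000 trials per cell (all splits are assumptions):

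| Region; stage (%) | N = 151 (PP) | N = 174 | N = 250 |
|---|---|---|---|
| equal thirds; equal thirds | 1% | 0.6% | 0.03% |
| 20/70/10; 20/35/45 | 19% | 15% | 5.5% |
| 10/85/5; 10/40/50 | 58% | 48% | 29% |

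Hand check at N = 174: the middle row is 1 − (1 − 0.12)(1 − 0.015)² ≈ 0.15, and the bottom row is 1 − (1 − 0.35)(1 − 0.12)² ≈ 0.50. A separate simulation of the middle row gave about 13%.

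**What steps 1–5 then return.** One simulated trial: N = 174, 23 non-responders, one region level of 15 patients all responders, unadjusted difference −0.034 (SE 0.051). The fit is unpenalised and the arm odds weight covariate levels equally:

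| Iterations | Coefficient of that level (SE) | Step 5 90% CI |
|---|---|---|
| 8 | 7.7 (26) | −0.28 to 0.27 |
| 12 | 11.7 (189) | about ±0.56 |
| 16 | 15.7 (1,398) | about ±1.09 |
| 25 | 24.7 (125,848) | about ±4.9 |

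Both arm proportions drift towards 1 (0.983 and 0.989 at 8 iterations). Weighting by the observed margins is worse: about ±2.1 at 12 iterations. Throughout, the treatment odds ratio stays at 0.683, with SE of its logarithm 0.459. Across separated trials with the middle split, the median step 5 SE was about 0.25, against about 0.05 for the crude difference.

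**Alternatives on the same trial.**
- Ordinary fit, risk difference standardised over the observed covariates: −0.043, SE 0.051, 90% CI −0.127 to 0.041.
- Firth fit through the unchanged steps: −0.031, SE 0.070, 90% CI −0.146 to 0.084.

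**The case against.** Several points against the concern stand.

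- **The treatment effect is not lost.** A reader might infer that the whole adjusted analysis collapses. It does not: the odds ratio and its CI stay finite, and only the conversion to a difference fails.
- **A choice after unblinding is not forced.** A reader might infer that any replacement would have to be picked with the code broken. An all-responder level is a property of pooled data and can be seen blinded. SAP 5.2 already plans a blinded look at ORR, and SAP 5.3 breaks the code only for the first CSR. The documents do not promise this check, but nothing prevents it.
- **Two premises are inferred.** The SAP says only that a logistic model is used, and the software name is redacted, so an unpenalised fit is the ordinary reading, not a stated fact. So is averaging over covariates. Odds read at one unseparated reference cell would be finite (0.822 and 0.872 in the example, CI −0.26 to 0.16), but they would describe a single stratum, and the SAP does not say this.
- **Few events per effect is not itself a failure.** The trigger is an all-responder level, and the planned pooling makes one less likely.
- **The ORR need not exceed 88%.** Using best response up to Month 7 may raise it. However, ITT patients without response data stay in the denominator as Missing (SAP 5 and 10.1.1), which lowers it.
- **Firth alone is not a full remedy.** Through the unchanged steps, with region 10/85/5 and stage 10/40/50, its mean SE was about 0.09, against 0.05 for the crude difference. Its 90% CI fell within ±17% in 40% of trials, against 92% for the crude interval.

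None of this removes the gap: where the event occurs, the interval described in steps 1–5 is unusable, and the SAP names no alternative.

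**Conclusion.** The point holds as a limited one. Under the ordinary reading (maximum-likelihood fit, arm odds averaged over covariate levels), a region or stage level without non-responders makes the step 5 interval an artefact of the stopping rule. At an ORR of 88% and N = 174 the chance is under 1% with equal thirds, about 13–15% with a smallest level of 10%, and about 50% with a smallest level of 5% and two others of 10%. It is somewhat higher in PP and lower at 250 patients. The documents give no stratum shares, so this range cannot be narrowed.

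A reader might infer that the similarity conclusion is at risk. It is not: SAP 10.1.1 rests that decision on the exact binomial CI, which does not use this model. What is at stake is whether the one stratification-adjusted check yields a usable interval on the scale of the margin. The weakness lies mainly in building the difference from undefined arm-level odds, and only secondarily in the lack of penalisation.

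**What to change.** In SAP 10.1.2, keep the covariate model and replace steps 1–5 with a standardised risk difference. Predict every patient's response probability under each treatment, average over the observed covariates, take the difference, and form the 90% CI by the delta method from the full covariance matrix of the coefficients. In simulation this gave usable, near-nominal intervals even with an all-responder level.

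Add that pooled blinded response will be tabulated by region, stage and age before the code is broken, and that a Firth-penalised fit of the same model will be used if any level contains only responders. Apply the rule to both ITT and PP.

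The cost is a short SAP change and slightly more programming. Where Firth is used, there is also slight shrinkage and a slightly wider CI.
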